4.2.1.1. Vitreous Haze

Dilated indirect ophthalmoscopy will be performed to assess retinal and choroid appearances and vitreous haze for study eye and fellow eye at all study visits.

[figure not shown]
The following scale will be used to define the extent of vitreous haze.

Vitreous Haze Grading Scale

Absent	Clear view of optic disc, retinal vessels and nerve fiber layer
Trace	Slight blurring of optic disc margin and of normal striations and reflex of nerve fiber layer
1+	Mild blurring of optic disc margin and slight loss of retinal vessel definition
2+	Moderate blurring of optic disc margin and loss of retinal vessel definition
3+	Optic nerve head and large vessels visible but borders quite (very) blurry
4+	Optic nerve head obscured

The diagram below presents the scoring convention that will be used to identify a minimum of “> 2 step increase” of vitreous haze for the primary efficacy endpoint.

Vitreous Haze Scoring Convention

* Nussenblatt et al 1985

4.2.1.2. Measurement of BCVA by ETDRS

Visual acuity testing in this study is required at a distance of 4 meters, and for subjects with reduced vision at 1 meter. Visual acuity is always tested with the subject's best correction and should be measured prior to pupil dilation and slit lamp biomicroscopy examination or any drops or ointments being used. BCVA by ETDRS will be measured at every study visit.

4.2.2. Analytical Approach for Primary Efficacy Endpoint

The recurrence of uveitis rate will be summarized with the number and percentage of subjects with the recurrence and 95% confidence interval (CI) based on binomial distribution using the Clopper-Pearson (Exact) method.

The vitreous haze score and measurement of BCVA results will be summarized by treatment group at each scheduled visit. Mean change from baseline and proportion of subjects who have an increase of vitreous haze score of ≥ 2 steps, and proportion of subjects who have a deterioration of at least 15 letters BCVA from baseline will be presented at each scheduled visit.

Abnormal vitreous haze for the study eye and fellow eye will be summarized by treatment group and visit.

4.2.3. Sensitivity Analysis

No sensitivity analysis will be performed.

4.3. Secondary Endpoints Analysis

4.3.1. Definition of Secondary Endpoints

The secondary efficacy endpoints will include the following endpoints:

4.3.1.1. Proportion of subjects who have a recurrence of uveitis in the study eye within 52 weeks

The recurrence of uveitis will be assessed the same as the primary efficacy endpoint within 52 weeks.

4.3.1.2. Mean change from baseline in BCVA letter score in the study eye at 24 and 52 weeks

The change from baseline in BCVA as measured by ETDRS letter at each visit will be calculated.

4.3.1.3. Number of recurrences of uveitis within 24 and 52 weeks

The recurrences of uveitis on the study eye will be assessed as described in the primary efficacy endpoint and the incidence will be counted.

4.3.1.4. Proportion of subjects with resolution of macular edema as measured by SD-OCT imaging at Day 28 and at Months 2, 3, 6, 9, and 12.

The number and percentage of subjects who had macular edema from SD-OCT imaging will be summarized for each assessment timepoint through Week 24 and Week 52.

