Eligibility determination, informed consent, demographics, medical and ophthalmic history (including a detailed history of the management of their uveitis over the previous 52 weeks), vital signs, clinical laboratory testing, ophthalmic examinations (includes BCVA, IOP, dilated ophthalmoscopy, and anterior, posterior and intermediate slit lamp examination), subjective ocular tolerability and discomfort assessment, concomitant medications, and pregnancy testing as appropriate.

Treatment Day (Day 1):

Eligibility confirmation including meeting the entry criteria for anterior chamber cells, vitreous haze, IOP, and visual acuity on Study Day 1, and then randomization to either intravitreal Yutiq 0.05 mg or sham injection. Following determination of study eye, subjects will receive either Yutiq 0.05 mg or the sham injection. Assessments on that day will include vital signs, ophthalmic examinations, spectral-domain – optical coherence tomography (SD-OCT), subjective ocular tolerability and discomfort assessment, pregnancy test if appropriate, concomitant medications, and adverse events (AEs).

Follow-up Visits:

Following injection on Study Day 1, subjects who were treated with Yutiq 0.05 mg will return for study visits on Days 7, 28, and at Months 2, 3, 6, and 12. Evaluations on these days will include: review of concomitant medications, vital signs, ophthalmic examinations, IOP, SD-OCT, subjective ocular tolerability and discomfort assessment, and AEs. All subjects treated with Yutiq 0.05 mg in the study will be followed for 52 weeks. In early May 2022, those subjects who had been treated with sham injection were discontinued from the study. Sham-treated subjects subsequently had their End of Study (EOS) evaluation.

Masking: Study subjects will receive either Yutiq 0.05 mg or a sham injection. Subjects and study staff conducting clinical study assessments, except for the clinician performing the injection procedure, will be masked to randomized treatment assignment.

Concomitant Medications:

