3 INVESTIGATIONAL PLAN

3.1 Overall Study Design

[figure not shown]
The protocol was originally planned to be a 52-week, prospective, randomized, masked (subject and outcome assessor), controlled, safety and efficacy study of intravitreal Yutiq 0.05 mg compared to sham injection with a primary efficacy and safety readout at 24 weeks.

The Sponsor has decided to stop enrollment for reasons other than safety or efficacy in early May 2022, following FDA advice received on January 24, 2022. The Sponsor is reevaluating the development program of Yutiq 0.05 mg. Subject enrollment has been stopped, and all subjects have been unmasked. Subjects who were randomized to the sham injection were discontinued from the study and underwent their EOS visit. Subjects who were randomized to sham injection may have been treated with standard of care medication, if necessary. Subjects who were randomized to Yutiq 0.05 mg will be followed on a modified protocol schedule through Month 12 (or ET) and evaluated for efficacy and safety.

As depicted in [Figure 3-1](#), subjects will receive either Yutiq 0.05 mg or a sham injection on Day 1 of the study. Subjects who were treated with Yutiq 0.05 mg will be assessed over the following 52 weeks on a modified protocol schedule according to the schedule presented in

Table 5–1. Subjects who were randomized to the sham injection were discontinued from the study and underwent their EOS visit.

Figure 3-1: Study Design Schema, Study EYP-2102-001

Note: The sponsor decided to stop enrollment for reasons other than safety or efficacy in early May 2022, following FDA advice received on January 24, 2022. The Sponsor is reevaluating the development program of Yutiq 0.05 mg. Subject enrollment in the study has been stopped. All subjects who were currently enrolled have been unmasked. Subjects who were to receive Yutiq 0.05 mg will be followed on a modified protocol schedule through Month 12 (or ET).

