6.1.	Appendix 1: List of Abbreviations.....	22
6.2.	Appendix 2: Supporting Study Information.....	23
6.2.1.	Disposition of Subjects.....	23
6.2.2.	Demographics.....	23
6.2.3.	Baseline and Disease Characteristics	23
6.2.4.	Protocol Deviations	23
6.2.5.	Medical History and Concurrent Illnesses	23
6.2.6.	Prior/Concomitant Medications	23
6.3.	Appendix 3: Data Handling Conventions	25
6.3.1.	Missing Date Imputation	25
7.	References	27

Version History

SAP Version	Date	Change	Rationale
1.0	08MAY2023	Not applicable	Original version

1. Introduction

This document presents the statistical analysis plan (SAP) for the protocol EYP-2102-001, a phase 3, multicenter, prospective, randomized, masked, controlled, safety and efficacy study of fluocinolone acetonide (FA) intravitreal 0.05 mg insert (Yutiq 0.05 mg) in subjects with chronic non-infectious uveitis affecting the posterior segment of the eye.

This SAP was developed in accordance with ICH E9 guideline. This SAP is to provide details of the statistical analyses based on the protocol version 3.0, dated July 20, 2022. The SAP will be finalized prior to database lock. Any deviations from the SAP after database lock and reasons for such deviations will be described and documented in the clinical study report.

The Sponsor decided to stop enrollment in early May 2022. Subjects who were randomized to Yutiq 0.05 mg will continue to be monitored on a modified-protocol schedule. The subjects who had been treated with sham injection were discontinued from the study. Consider the fact that the study was terminated early, the analyses described in this SAP has been limited to the scope per the interest of EyePoint Pharmaceuticals, Inc. For such a reason, the list of endpoints and analyses in this SAP is a reduced list from the study protocol.

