3.1. Intent-to-Treat Analysis Set

The Intent-to-Treat (ITT) analysis set will include all subjects who are randomized. Subject will be classified according to the assigned treatment. The ITT set will be used for analysis of efficacy, unless otherwise specified.

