4.2. Primary Efficacy Endpoint Analysis

4.2.1. Definition of Endpoint

The primary efficacy endpoint is the proportion of subjects who have a recurrence of uveitis in the study eye within 24 weeks (6 months) after receiving study treatment. Recurrence is defined as:

- An increase in the vitreous haze of ≥ 2 steps compared to baseline at the Week 24 visit, or any visit time point prior to the Week 24 visit after the Study Day 7 visit

Or

- A deterioration in visual acuity of at least 15 letters BCVA compared to baseline at the Week 24 visit, or any visit time point prior to the Week 24 visit after the Study Day 7 visit.

Any criterion used to define recurrence must be attributable only to noninfectious uveitis. To prevent post-procedural inflammatory reactions from being reported as uveitis recurrences, assessments for recurrence of uveitis begin after the Study Day 7 visit.

The study protocol stated to impute subjects who don't complete Week 24 eye examinations and subjects who take prohibited medications as having a recurrence. Consider the fact that the study was terminated early, no imputation will be implemented. Summary of the primary efficacy endpoint will be based only on the observed data from the subjects who reached Week 24.

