4.3.2. Analytical Approach for Secondary Efficacy Endpoints

The secondary efficacy analyses will be conducted using the ITT analysis set based on observed data.

- The proportion of subjects with recurrent of uveitis will be summarized for the timepoint of interest using the same method described for the primary efficacy endpoint.
- The mean change from baseline in BCVA as measured by ETDRS letter score at each visit will be summarized for week 24 and 52 using descriptive statistics.

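### The number of recurrences within 24 and 52 weeks has no stated denominator or exposure term, although sham follow-up was cut short and Yutiq follow-up was not

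*SAP*

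**What the plan says.** SAP 1.1 lists the number of recurrences within 24 and 52 weeks as a secondary efficacy endpoint. Its definition in SAP 4.3.1.3 is a single sentence: "The recurrences of uveitis on the study eye will be assessed as described in the primary efficacy endpoint and the incidence will be counted".

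SAP 4.3.2 adds the analysis set: "The secondary efficacy analyses will be conducted using the ITT analysis set based on observed data". SAP 3.1 defines that set: "The Intent-to-Treat (ITT) analysis set will include all subjects who are randomized". The two bullets in SAP 4.3.2 cover the recurrence proportion and the change in BCVA. Neither covers the count.

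The primary endpoint to which SAP 4.3.1.3 refers has its own restriction in SAP 4.2.1: "Summary of the primary efficacy endpoint will be based only on the observed data from the subjects who reached Week 24". The SAP does not say whether this restriction carries over to the count.

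Follow-up differs by arm. The Protocol Synopsis (Follow-up Visits) states: "In early May 2022, those subjects who had been treated with sham injection were discontinued from the study". Protocol 3.1 keeps Yutiq subjects under observation to Month 12 or early termination.

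**The concern.** A count over a fixed horizon compares two arms fairly only if both were observed for that horizon or if the count is divided by time observed. Here the sponsor's decision shortened observation in one arm only, and summaries are to be shown by treatment group (SAP 4.1.1). A reader could take a short sham observation period for a low recurrence frequency.

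Two protocol provisions that would have dealt with incomplete follow-up in some way are no longer in force. Time to recurrence (Protocol 10.2) is not in the SAP's endpoint list. The rule that imputes a recurrence when the Week 24 or Week 52 examination is missing (Protocol 11.4.4) is withdrawn in SAP 4.2.1. SAP 4.2.3 plans no sensitivity analysis for the primary endpoint, and none is described for the count.

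**Working it through.** The documents give no recurrence count, rate or person-time for this endpoint, so there is no figure to reproduce. The check asks what the unspecified count would show under each of the two available readings.

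**Inputs from the documents.** Recurrences are assessed after the Day 7 visit (SAP 4.2.1). Full time at risk is therefore 168 − 7 = 161 days to Week 24 and 364 − 7 = 357 days to Week 52. Allocation is 1:1 (SAP 1.2.1).

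**Assumptions.** Sham dosing was spread evenly over the W days before the stop, with W = 180 (range 120 to 240). Yutiq subjects are observed in full. Recurrence rates are constant, at 1.0 per year on sham and 0.3, 0.5 or 0.7 per year on Yutiq.

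**Reading 1: mean over all ITT subjects**

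Mean sham time at risk is the average of min(follow-up, horizon) − 7 days, floored at zero.

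- 52 weeks, W = 180: 173² / (2 × 180) = 83.1 days, or 23% of 357.
- 24 weeks, W = 180: (161²/2 + 12 × 161) / 180 = 82.7 days, or 51% of 161.
- For W from 120 to 240, the shares are 15% to 32% at 52 weeks and 33% to 64% at 24 weeks.

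The expected count per subject is rate × days / 365.25.

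| Horizon | Sham, W = 180 (W = 120 to 240) | Yutiq, ratio 0.3 | Yutiq, ratio 0.5 | Yutiq, ratio 0.7 |
|---|---|---|---|---|
| 24 weeks | 0.23 (0.15 to 0.28) | 0.13 | 0.22 | 0.31 |
| 52 weeks | 0.23 (0.15 to 0.31) | 0.29 | 0.49 | 0.68 |

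The apparent Yutiq/sham ratio equals the true ratio multiplied by Yutiq time over sham time. With W = 180 the multiplier is 161/82.7 = 1.95 at 24 weeks and 357/83.1 = 4.29 at 52 weeks, whatever the sham rate. Raw counts therefore favor sham when the true ratio exceeds the sham share of time at risk: 0.51 at 24 weeks and 0.23 at 52 weeks.

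**Second calculation with different assumptions.** Take a sham rate of 0.6 per 23 at-risk weeks, a ratio of 0.5, mean sham follow-up of 12 weeks and 15 subjects per arm.

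- Sham: 0.6 × 11/23 = 0.29 per subject.
- Yutiq: 0.30 to Week 24 and 0.30 × 51/23 = 0.67 to Week 52.
- With Poisson totals, the chance that the sham total is no higher than the Yutiq total is 0.59 for the 24-week count and 0.95 for the 52-week count. With full 24-week sham follow-up, the 24-week chance would be 0.14.
- Break-even mean sham follow-up is 1 + ratio × (horizon − 1) weeks. For ratios 0.3, 0.5 and 0.7 this is 7.9, 12.5 and 17.1 weeks for the 24-week count, and 16.3, 26.5 and 36.7 weeks for the 52-week count.
- Dividing by person-time returns 0.60 against 0.30 per 23 at-risk weeks, the true ratio of 0.5.

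**Reading 2: only subjects who reached the horizon**

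Taking 5 May 2022 as the stop date (the documents say only early May), a sham subject reaches 168 days only if dosed by 18 November 2021, and 364 days only if dosed by 6 May 2021. Using the full 28-day early window for Months 6 and 12 (Protocol Table 5-1), these become 16 December and 3 June 2021. With W = 180, the share of sham subjects with 168 days is 12/180 = 7%, or 40/180 = 22% with the window, and none reaches Month 12. Recurrences seen in the other sham subjects would not be counted.

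**The case against.** The strongest reply is that the SAP does not prescribe a biased count. A reader might infer that sham subjects are scored as recurrence-free for the weeks after they left. The text does not say so: SAP 4.1.1 bases summaries on observed data and SAP 4.1.4 generally imputes nothing. Zeros arise only if someone totals or averages over all randomized subjects. The cross-reference to the primary endpoint can equally be read as importing its limit, "based only on the observed data from the subjects who reached Week 24", which removes them. This stands, and it is why the point is a missing specification with two possible consequences.

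A second reply is that reversal is not established. This also stands. At a ratio of 0.3 and W = 180, the 24-week counts are 0.23 against 0.13, so sham still looks worse. At 0.3 and W = 240, the 52-week counts are 0.31 against 0.29, with no reversal. The 52-week Yutiq figures also assume that every episode is detected, although no visit is scheduled between Months 6 and 12.

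A third reply is that nothing is tested and follow-up is shown elsewhere: subjects remaining at each visit (SAP 4.4.1), duration of participation (SAP 6.2.1) and listings. That limits the harm, but none of these tables adjusts the count or is linked to it.

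A rate has weaknesses too. Sham time falls mostly in the early, densely visited period, and risk may not be constant, because prior uveitis treatment is ended within 12 weeks of Day 1 (Protocol Synopsis, Concomitant Medications).

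**Conclusion.** The concern holds as a gap in specification. SAP 4.3.1.3 and 4.3.2 give no denominator and no exposure term for a count whose observation time differs by arm. Neither available reading gives a fair comparison. The ITT total or mean understates sham relative to Yutiq. The completer count drops early sham events and may leave few or no sham subjects at 52 weeks.

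Under the ITT reading the true difference can shrink, disappear or, mainly at 52 weeks, reverse. With W = 180, the sham and Yutiq counts at a ratio of 0.5 are 0.23 against 0.22 at 24 weeks and 0.23 against 0.49 at 52 weeks. At 0.3 they are 0.23 against 0.13 and 0.23 against 0.29. These figures rest on assumed dosing dates, rates and constant risk. Actual enrollment dates, sample size and recurrence rates are not in the documents.

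It would be tempting to conclude that the sham arm will look better than Yutiq. The documents do not support that as a prediction. No hypothesis test is affected, because the SAP plans none. The correction should still be made, because the summary as written can mislead and a better one is cheap.

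**What to change.** In SAP 4.3.1.3 and 4.3.2:

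- State the denominator: all ITT subjects with at least one eye examination after the Day 7 visit.
- Report by arm the number of study-eye recurrences, the subject-years observed, and recurrences per subject-year. Subject-years run from the Day 7 visit to the last eye examination, capped at Month 6. Name the early termination and end-of-study examinations as included, since SAP 4.1.3 bases tables on nominal visits.
- Give an exact Poisson 95% CI for each rate, with a note that it ignores repeat episodes within a subject.
- Report the period after Month 6 separately, as Yutiq only unless some sham subjects were followed that long.
- Do not show an unadjusted sham count or mean under a 24- or 52-week label.

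The cost is a few lines of SAP text and one small table. The dates and examinations are already collected, because Protocol 5.1.7 includes BCVA and the ocular examination at early termination. Two limits should be stated beside the table: the rate assumes roughly constant risk although prior therapy is ended within 12 weeks of Day 1, and visits are sparse after Month 3. If the database is already locked, the change belongs among the deviations that SAP 1 says will be documented in the clinical study report.

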4.3.2. Analytical Approach for Secondary Efficacy Endpoints

The secondary efficacy analyses will be conducted using the ITT analysis set based on observed data.

- The proportion of subjects with recurrent of uveitis will be summarized for the timepoint of interest using the same method described for the primary efficacy endpoint.
- The mean change from baseline in BCVA as measured by ETDRS letter score at each visit will be summarized for week 24 and 52 using descriptive statistics.

4.4. Safety Analyses

Safety data will include adverse events reported after screening, data collected from ocular examinations and IOP measurements, ocular tolerability and discomfort assessments, vital sign measurements, clinical laboratory tests, and the use of rescue and concomitant medications.

All safety analyses will be performed on the safety analysis set based on actual treatment received. Ocular safety data will be summarized on the study eye and fellow eye separately, where applicable.

4.4.1. Extent of Exposure

Subjects will receive either intravitreal Yutiq 0.05 mg or sham injection in the designated study eye on Day 1 and will be followed for 52 weeks after treatment for change in IOP and for endophthalmitis. The number and percentage of subjects who remain on the study will be summarized for each visit by treatment group. The number of subjects in each treatment group will be presented based on the actual treatment they have received.

4.4.2. Adverse Events

Adverse event data will be coded using the Medical Dictionary for Regulatory Activities (MedDRA). The severity of each AE will be graded by the investigator per CTCAE v5.0 criteria.

Descriptive statistics will be provided for all treatment-emergent adverse events (TEAEs). Both ocular and non-ocular TEAEs are defined as events that start after the study drug administration, and occur before termination of the study, or were present before study drug administration and worsened after dose administration.

Frequency counts and percentage of subjects within each treatment group will be provided by system organ class (SOC) and preferred term (PT) by treatment. Within each level of summarization (SOC, PT), subjects who experience more than one occurrence will only be counted once. Adverse events will also be presented by severity (mild, moderate, severe, life- or sight-threatening), and by relationship to study drug (not related, possibly related, probably related). Listings of deaths, and AEs leading to withdrawal will be presented.

Summaries will be sorted in descending order of frequency in the Yutiq 0.05 mg arm, when applicable. A listing of treatment-emergent AEs, treatment-emergent ocular events, and serious AEs will be provided.

Ocular Adverse Events

The following ocular events will be considered AEs for the purposes of this study:

- Decrease in BCVA of at least ≥ 15 letters or ≥ 3 lines from the previous BCVA measurement
- Moderate or severe (Grade 3 or 4) ocular findings compared to the last ocular examination
- Worsening of >2 steps in anterior chamber cell count or vitreous haze compared to the last ocular examination
- Increase in IOP of >10 mmHg at two visits at least 1 week apart or an increase in IOP to >25 mmHg

